XmAb18087 administration ^{e,f}	X	X	X	X	X	X	
Pembrolizumab administration ^f			X				
Physical examination	X	X	X	X	X	X	
Vital signs ^{j, k}	X	X	X	X	X	X	
Weight	X	X	X	X	X	X	
ECOG performance status ^h	X	X	X	X	X	X	
12-lead electrocardiogram (supine) ^{l,m}	X	X	X	X	X	X	
CBC w/ differential (absolute and percentage), platelet count ^h	X	X	X	X	X	X	
Chemistry panel ^h	X	X	X	X	X	X	
Coagulation panel ^{hl}	X	X	X	X	X	X	
Urinalysis	X			X			
Serum β -hCG (females of childbearing potential) FSH (postmenopausal) ⁿ	X			X			
Flow cytometry (blood) ^o				X		X	
Cytokine/inflammation panel ^p	X			X			
PK blood sampling ^t	X		X				
Immunogenicity (ADA) blood sampling ^{u,x}	X		X	X		X	
RECIST 1.1 tumor assessment ^v							X
Monitor/record adverse events	X	X	X	X	X	X	
Concomitant medications	X	X	X	X	X	X	

Version 1.0 Page 56 of 145

Table 7: **Schedule of Assessments (Continued)**

Evaluation or Procedure			Post-treatment	
Study Day	ЕОТ	14 d post-EOT	28 d post-EOT	Long-term Follow-up (6 & 12 mo after EOT)
NETSPOT Gallium 68 dotatate PET/CT scan ^{a,b}	X			
Medical history			X	
Physical examination	X	X	X	
Vital signs ^{i, k}	X	X	X	
Weight	X	X	X	
ECOG performance statush	X	X	X	
12-lead electrocardiogram (supine) l,m			X	
CBC w/ differential (absolute and percentage), platelet count ^h	X	X	X	
Chemistry panel ^h	X	X	X	
Coagulation panel ^h	X	X	X	
Urinalysis	X	X	X	
HBsAg, HBcAb, HCV, HIV	X			
Serum β–hCG (females of childbearing potential) FSH (postmenopausal) ⁿ	X		X	
Flow cytometry (blood) ^o	X	X	X	
Cytokine/inflammation panel ^p				
Polyoma virus assay (serum) ^q	X		X	
PK blood sampling ^t	X	X	X	
Immunogenicity (ADA) blood sampling ^{u,x}	X	X	X	
RECIST 1.1 tumor assessment ^v	X			
Monitor/record adverse events	X	X	X	
Concomitant medications	X	X	X	
Phone/email/mail contact for progression				X

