7.9.4. Post-treatment Follow-up Period (2 Weeks and 4 Weeks After EOT)

Subjects will have visits 14 days post-EOT and 28 days post-EOT. Assessments are as indicated in Table 7. Once these two visits have been completed, the subject will be considered as having completed participation in the clinical trial. If a subject enrolls into another trial or requires treatment before either of these scheduled visits, the visits may be performed earlier. If a subject is unable to return for any scheduled visits after the end of treatment, he/she will be considered as having completed study requirements at the end of treatment.

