11. ASSESSMENT OF SAFETY

Adverse event reporting will begin with the signing of the informed consent document (Screening) and will continue until the end of the subject's participation in the study: ie, until a subject has discontinued or completed the study.

Safety and tolerability assessments will include the following:

- AEs
- Vital signs
- PE findings
- Clinical laboratory safety assessments
- ECG parameters

Biomarkers of CRS (IL-2, IL-6, IL-8, IL-10, IFN- γ , IL-13, IL-1B, and TNF- α) will also be collected as additional safety information.

Details for management of hypersensitivity reactions, CRS, and neurologic toxicities are provided in Section 11.3.2, 11.3.3.3, and 11.3.3.4, respectively, as well as in Section 11.3.3 and Appendix C of this protocol.

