11.1.4. Adverse Events of Special Interest

IRAEs (Part B only) and infusion reactions (hypersensitivity reactions and CRS) are designated events of special interest in this protocol. Refer to Section 11.3.

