11.1.5. Reporting Serious Adverse Events

The Investigator will review each potential SAE and evaluate the intensity and the causal relationship of the event to IMP. All potential SAEs will be recorded from signing of informed consent until the end of the subject's participation in the study: ie, the subject has discontinued or completed the study, except for the long-term follow-up period. During the long-term follow-up period, only SAEs that come to the attention of the Investigator and that the Investigator believes to have a reasonable causal relationship to the IMP will be reported.

The Investigator is responsible for reporting SAEs related to pembrolizumab to regulatory authorities per reporting guidelines.

The Investigator is responsible for providing notification to ICON of any potential SAE, whether deemed IMP-related or not, that a subject experiences during his/her participation in study within 24 hours of becoming aware of the event. ICON will provide the information to the Sponsor.

The initial SAE form should be completed and emailed to with the following information:

- Study number
- Subject number
- Gender
- Year of birth
- Name of PI and full clinical site address
- Name of the reporter
- SAE event term
- Details of SAE
- Criterion for classification as "serious"
- Study drug name, dose, and treatment start date
- Date of SAE onset
- Date of SAE first awareness (by Investigator or study site staff)
- Causality assessment

[figure not shown]
Version 1.0 Page 84 of 145

18 August 2020

ICON will request clarification of omitted or discrepant information from the initial notification. The Investigator or an authorized delegate is responsible for providing the requested information to ICON within 24 hours of the request.

Initial reports of SAEs must be followed up as soon as possible with detailed descriptions; this may include clear photocopies of other documents as necessary (eg, hospital reports, consultant reports, autopsy reports, etc.) with the study subject's personal identifiers removed. All relevant information obtained by the Investigator through review of these documents will be recorded and forwarded to ICON within 24 hours of receipt of the information.

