Appendix D. DOSE MODIFICATION AND TOXICITY MANAGEMENT FOR IMMUNE-RELATED ADVERSE EVENTS

IRAEs may occur shortly after the first dose of pembrolizumab or up to several months after the last dose. Based on existing clinical data for pembrolizumab and other checkpoint inhibitors, most IRAEs were reversible and could be managed with dose interruptions, administration of corticosteroids, and/or other supportive care. For suspected IRAEs, ensure adequate evaluation to confirm etiology or exclude other causes. Additional procedures or tests such as bronchoscopy, endoscopy, or skin biopsy may be included as part of the evaluation. IRAEs known to be associated with pembrolizumab, as well as guidelines for dose modification and management when they occur, are described in the Keytruda Prescribing Information (Keytruda® Package Insert, 2020); these guidelines are summarized in Table 18.

For additional information on diagnosis and management of IRAEs, see the NCCN Guidelines – Management of Immunotherapy-Related Toxicities (Appendix E).

Version 1.0 Page 130 of 145

Table 18: Dose Modification and Toxicity Management Guidelines for Immune-Related Adverse Events in Patients Receiving Pembrolizumab

General Instructions:

- 1. Corticosteroid taper should be initiated upon AE improving to Grade 1 or less and continue to taper over at least 4 weeks.
- 2. For situations where pembrolizumab has been withheld, it can be resumed after AE has been reduced to Grade 1 or 0 and corticosteroid has been tapered.
- 3. For severe and life-threatening IRAEs, IV corticosteroid should be initiated first followed by oral steroid. Other immunosuppressive treatment should be initiated if IRAEs cannot be controlled by corticosteroids.

Immune-related AEs	Toxicity Grade or Conditions (CTCAE v5.0)	Action Taken with Pembrolizumab	IRAE Management with Corticosteroid and/or Other Therapies	Monitor and Follow-up
Pneumonitis	Grade 2	Withhold	Administer corticosteroids (initial dose of	Monitor participants for signs and symptoms of pneumonitis Evaluate participants with
	Grade 3 or 4, or recurrent Grade 2	Permanently discontinue	1 - 2 mg/kg prednisone or equivalent) followed by taper	suspected pneumonitis with radiographic imaging and initiate corticosteroid treatment Add prophylactic antibiotics for opportunistic infections

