Recognizing Immune-Related Symptoms

Onset of irAEs can be immediate or delayed by as much as 2 years, and can affect any organ system.²⁵ Early

bCloser monitoring may be required for patients with combination immunotherapy regimens. Refer to prescribing information for each individual immunotherapy agent for monitoring recommendations.

^c After first four doses of immunotherapy, only as clinically indicated.

Version 1.2020 © National Comprehensive Cancer Network, Inc. 2020. All rights reserved.

The NCCN Guidelines® and this illustration may not be reproduced in any form without the express written permission of NCCN.

ICI GI-1

recognition of symptoms and prompt intervention are key goals for the successful management of immunotherapy-related toxicity. When encountering one or more of these symptoms, asking appropriate questions can help discern whether the patient is experiencing a symptom due to disease progression, an infection, some other condition, or an irAE. Symptoms that may cause clinical suspicion of an irAE include (main symptoms are bold and underlined; associated symptoms are underlined; possible irAE type/diagnoses are in italics):

- Change in bowel pattern compared with baseline, especially if it is watery diarrhea, stool contains blood or mucus, or cramping or severe abdominal pain develop, may indicate *colitis*. However, blood in the stools and/or fever may be because of other causes of gastrointestinal bleeding, such as *infection* or *peptic ulcer disease* or *bleeding due to tumor*.
- Cough may be due to an upper respiratory infection, but especially if the cough is dry or is coupled with shortness of breath, it could indicate *pneumonitis*.
- Headaches can be indicative of brain metastases, but when presenting with fatigue, visual symptoms, nausea, and other symptoms, may be indicative of *hypophysitis*

- (inflammation of the pituitary). ²⁶ ²⁸ Headaches may also be indicative of *meningitis* when coupled with a stiff neck, photophobia, nausea, or fever. Headaches can also be indicative of *encephalitis* if coupled with fever, tiredness, confusion, mood change, memory problems, stiff neck, and other symptoms. Headaches, head pain, and scalp tenderness, may be indicative of *giant cell arteritis*.

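### In Part B, new immune-related AEs are not actively solicited after the 28-day post-treatment visit (55 days after the last pembrolizumab dose in a completed cycle), although the protocol says they may start months later

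*Protocol*

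**What the plan says.** Protocol 11.1.4 states that "IRAEs (Part B only) and infusion reactions (hypersensitivity reactions and CRS) are designated events of special interest in this protocol". On timing, Appendix D says "IRAEs may occur shortly after the first dose of pembrolizumab or up to several months after the last dose", and the guideline reproduced in Appendix E says "Onset of irAEs can be immediate or delayed by as much as 2 years".

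Protocol Section 11 collects AEs from consent "until a subject has discontinued or completed the study". Section 7.9.4 fixes that end point at the 14- and 28-day post-EOT visits: "Once these two visits have been completed, the subject will be considered as having completed participation in the clinical trial". A subject who cannot return after treatment stops sooner: "he/she will be considered as having completed study requirements at the end of treatment". In Table 7 (Section 7.9), AE monitoring runs to the 28-day visit. The only entry in the long-term column is "Phone/email/mail contact for progression", and 7.9.5 describes the 6- and 12-month contacts as collecting progression and survival.

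For the long-term period, 11.1.5 limits reporting to "only SAEs that come to the attention of the Investigator and that the Investigator believes to have a reasonable causal relationship to the IMP". Its next paragraph makes the Investigator responsible for reporting pembrolizumab-related SAEs to regulatory authorities and states no end date. The duty to notify ICON, which passes reports to the sponsor, covers any potential SAE, but only during participation.

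**The concern.** The protocol names IRAEs as events of special interest, states a latency for them, and then closes routine collection at a point that this latency can exceed. The schedule already contains two later contacts, but neither asks about AEs.

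Safety is a primary objective of Part B, which gives a T-cell-engaging bispecific together with an anti-PD1 antibody. Its safety tables would describe IRAEs that begin before participation ends and would under-count later ones. A reader of those tables could take the observed IRAE profile as complete when its right-hand edge is set by the visit schedule.

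**Working it through.** The plan gives no figure for the interval from the last pembrolizumab dose to the last AE visit, so there is nothing to reproduce. The interval follows from the schedule. Visit windows of ±2 days are ignored.

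**Inputs**
- Cycle length 42 days; pembrolizumab on Day 15 (Protocol 7.3).
- EOT visit at the end of the last cycle (Day 42), or on the day of termination if earlier (7.9.3.3).
- Last AE visit 28 days after EOT (7.9.4, Table 7).
- XmAb18087 in Part B on Days 1, 8, 22, 29 and 36 (7.3).
- For premature discontinuers, post-treatment evaluations are due within 4 weeks of the last XmAb18087 dose (8.8).
- Section 10.2.1 gives pembrolizumab on Days 15 and 36; 7.3, Table 3 and 10.4.4 give Day 15 only.

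**Interval = (EOT day − last pembrolizumab day) + 28**

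| Case | Calculation | Days |
|---|---|---|
| Completed cycle | 42 − 15 + 28 | 55 |
| EOT on the infusion day | 15 − 15 + 28 | 28 |
| EOT on Day 14 of the next cycle | 56 − 15 + 28 | 69 |
| Completed cycle, Day 36 dose (10.2.1) | 42 − 36 + 28 | 34 |

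**Under the 8.8 limit, interval = (last XmAb18087 day + 28) − 15**
- EOT on Day 15, last XmAb18087 on Day 8: 8 + 28 − 15 = 21 days.
- EOT on Day 14 of the next cycle, last XmAb18087 on study Day 50: 50 + 28 − 15 = 63 days.

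**Departures from schedule**
- Subject cannot return after EOT: 42 − 15 = 27 days after a completed cycle, or 15 − 15 = 0 if EOT is the infusion day.
- Pembrolizumab withheld in the last cycle (allowed by Table 18): 84 − 15 + 28 = 97 days.

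**Next contact.** Counting from EOT as in Table 7, and taking 6 months as 183 days and 12 months as 365, the contacts after a completed cycle fall 42 − 15 + 183 = 210 and 42 − 15 + 365 = 392 days after the last dose. The first is 210 − 55 = 155 days after the last AE visit.

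**Part of the stated latency not actively covered.** The documents do not quantify several months. If it means 3 to 6 months (91 to 183 days; my assumption):
- Completed cycle: 91 − 55 = 36 to 183 − 55 = 128 days.
- On-schedule range of 28 to 69 days: from 91 − 69 = 22 to 183 − 28 = 155 days.
- 8.8 range of 21 to 63 days: from 91 − 63 = 28 to 183 − 21 = 162 days.
- Day 36 dose: 91 − 34 = 57 to 183 − 34 = 149 days.

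**Subjects concerned.** The Part B maximum is 4 run-in cohorts × 6 + 30 = 54. SAP 5.1 reports 4 subjects enrolled, 2 in Part A and 2 in Part C, so none in Part B.

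**The case against.** The strongest reply is that serious events are not left uncovered. After participation ends, a related SAE that reaches the Investigator is still reportable under 11.1.5, and the same section gives the Investigator a separate, open-ended duty to report pembrolizumab-related SAEs to regulators. An IRAE that starts inside the window is followed until it resolves or stabilizes (11.1.2, 11.1.6). All of this stands. It narrows the gap to new late events: non-serious ones, which have no route, and serious ones, which depend on someone telling the Investigator.

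A reader might go further and infer that late pembrolizumab-related SAEs fall outside 11.1.5 because the IMP means XmAb18087 alone. Section 7.10.2 uses the term for the product the sponsor is developing, and sites supply pembrolizumab as standard of care. The documents do not settle this. Section 14.6 plans summaries of treatment-related events for pembrolizumab where the drugs can be distinguished, while the causality assessment in 11.1.2.2 is worded only for the IMP, which suggests the term was meant to cover both. What can be said is that, after participation ends, no explicit route takes a pembrolizumab-related SAE to the sponsor.

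The onset evidence is also mixed. The 2-year figure in Appendix E has no stated reference point and need not mean time since the last dose. The same appendix gives early figures: colitis typically within 6 to 8 weeks of starting treatment, and a median of 34 days from initiation in one myocarditis series. Many IRAEs would therefore fall inside the window. These figures run from the start of treatment and do not give the proportion starting after the last dose, so they limit the likely loss without removing the late events that Appendix D describes.

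Finally, pembrolizumab is given at an approved dose (5.2.3), and a short post-treatment AE window can be defended. However, 11.1.4.2 already sets a 120-day window for pregnancy reports, so longer collection was workable here.

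**Conclusion.** The point holds as a limit on coverage in the Part B design. With the Day 15 dose, active solicitation of new IRAEs ends 55 days after the last pembrolizumab dose in a completed cycle, and 28 to 69 days after it across on-schedule stopping days. The two conflicting passages, 8.8 and 10.2.1, shorten this to 21 to 63 days for premature discontinuers and to 34 days after a completed cycle. The main longer case is a withheld last dose, at 97 days.

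The number of events missed cannot be computed, because the documents give no incidence of late IRAEs. The figure of 36 to 128 uncovered days after a completed cycle rests on reading several months as 3 to 6.

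A reader might infer that a primary endpoint is wrongly defined. It is not: the TEAE definition in 14.6 has no end date, and the collection window simply bounds what can be counted. A reader might also infer that reported safety results are biased. They are not, since no Part B subject was enrolled. What remains is an inexpensive improvement for anyone reusing this protocol.

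**What to change.** For Part B:

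1. In 7.9.5 and the Table 7 long-term column, ask about new immune-related AEs at the existing 6- and 12-month contacts. Record term, grade, onset date, seriousness, and any new anticancer therapy with its start date.
2. List IRAEs by onset before and after the 28-day post-EOT visit, so that the two levels of ascertainment are not mixed.
3. Optionally, state in 11.1.5 that pembrolizumab-related SAEs in long-term follow-up also go to the sponsor through ICON.

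The cost is one question and one eCRF page at contacts already planned, one extra listing and, if adopted, one sentence in 11.1.5. No visit is added.

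The information would be imperfect. Grade and onset would be recalled by phone, email or mail, up to 155 days after the last AE visit at the first contact following a completed cycle. Attribution is less certain once another therapy has started. Some subjects will not be reached, because 7.4.2 and 8.8 may end follow-up when new therapy begins.

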11.1.6. Follow-up of Adverse Events

All AEs experienced by a subject, irrespective of the suspected causality, will be monitored until the event has resolved or stabilized, until any abnormal laboratory values have returned to baseline or stabilized at a level acceptable to the Investigator and Sponsor medical representative, until there is a satisfactory explanation for the changes observed, or until the subject is lost to follow-up.

11.1.7. Treatment/Reporting of Overdose

In the event of an overdose, the physician should:

- Contact the Medical Monitor immediately
- Closely monitor the subject for any AE/SAE and laboratory abnormalities
- Obtain a plasma PK sample if requested by the Medical Monitor (determined on a case-by-case basis)
- Document the quantity and duration of the excess dose

Decisions regarding dose interruptions or modifications will be made by the Investigator in consultation with the Medical Monitor based on the clinical evaluation of the subject.

Version 1.0 Page 85 of 145

All overdose cases should be reported as SAEs.

11.2. Investigational New Drug Safety Reports

During the course of the study, the Sponsor may determine that certain safety reports are required to comply with regulations. The PI may receive a letter called an "Investigational New Drug (IND) Safety Report." These reports must be submitted to the IRB per local requirements as soon as possible, and documentation of this submission should be available to the Sponsor or ICON.

11.3. Guidelines for Prophylaxis and Management of Hypersensitivity Reactions, Cytokine Release Syndrome, and Neurological Toxicity Attributed to XmAb18087

Because administration of XmAb18087 has been associated with symptoms of infusion reaction/CRS in some subjects, it is required that all subjects receive the following medications before at least the first 4 doses of XmAb18087:

[figure not shown]
- a. Acetaminophen (Tylenol®): 650 mg PO once before dosing with XmAb18087
- b. Diphenhydramine (Benadryl®): 50 mg PO once before dosing with XmAb18087
- c. 10 to 20 mg IV dexamethasone (Decadron®) before dosing with XmAb18087

If a subject receives 4 consecutive doses of XmAb18087 without ≥ Grade 1 infusion reaction/CRS, the prophylaxis described above may be modified, prophylactic medications are to be administered to all subjects before at least the first 4 doses of the study drug.

11.3.1. Introduction and Grading

Grading of toxicity, including allergic/hypersensitivity reactions, is by CTCAE version 5.0, except for CRS, which is graded using the American Society for Transplantation and Cellular Therapy (ASTCT) CRS Consensus Grading (Lee, 2019) See Table 10 for these definitions.

All sites should review and implement the general guidelines for the use of tocilizumab and IV fluids discussed below in Sections 11.3.3.1 and 11.3.3.2. Otherwise, management of CRS and other infusion-related reactions should be per standard investigational site procedures. Or, if there are no local standards or if they are incomplete, the approaches discussed here may be used.

Version 1.0 Page 86 of 145

Table 10: American Society for Transplantation and Cellular Therapy Cytokine Release Syndrome Consensus Grading

CRS Parameter	Grade 1	Grade 2	Grade 3	Grade 4	
Fever ^a	Temperature ≥ 38 °C	Temperature ≥ 38 °C	Temperature ≥ 38 °C	Temperature ≥ 38 °C	
			With		
Hypotension	None	Not requiring vasopressors	Requiring a vasopressor with or without vasopressin	Requiring multiple vasopressors (excluding vasopressin)	
			And/or ^b		
Нурохіа	None	Requiring low-flow nasal cannula ^c or blow-by	Requiring high-flow nasal cannula c, facemask, nonrebreather mask, or Venturi mask	Requiring positive pressure (eg, CPAP, BiPAP, intubation and mechanical ventilation)	

BiPAP = bilevel positive airway pressure; CPAP = continuous positive airway pressure; CRS = cytokine release syndrome; CTCAE = Common Terminology Criteria for Adverse Events.

Organ toxicities associated with CRS may be graded according to CTCAE v5.0, but they do not influence CRS grading.

11.3.2. Cytokine Release Syndrome Versus Allergic or Hypersensitivity Reactions

Cytokine release syndrome is mechanistically different from allergic/hypersensitive reactions (Lee, 2019), although some of the manifestations are common to both AEs and both have been reported to occur with therapeutic antibodies. An acute infusion reaction is often caused by a type 1 hypersensitivity mechanism due to immunoglobulin-E (IgE)-mediated release of histamines and prostaglandins, although a direct interaction with mast cells and basophils can also occur. It is less clear how cytokine release is triggered, although it is likely to be associated with immune cell activation; in this case, there is evidence that immunologic cascade is initiated by triggering of CD3-expressing T lymphocytes, resulting in TNF- α mediated monocyte/macrophage activation and systemic toxic cytokine release (Li, 2019).

Signs and symptoms usually develop during or shortly after drug infusion in hypersensitivity reactions, are more likely to occur after several doses of the drug and are largely related to histamine release. Typical signs and symptoms of hypersensitivity reaction include rash/urticaria, flushing, pruritus, fever, dyspnea, cough, and hypotension, although the following may also occur (Lenz, 2007):

Arthralgia

Version 1.0 Page 87 of 145

^a Fever is defined as temperature ≥ 38 °C not attributable to any other cause. In patients who have CRS then receive antipyretic or anticytokine therapy such as tocilizumab or steroids, fever is no longer required to grade subsequent CRS severity. In this case, CRS grading is driven by hypotension and/or hypoxia.

^b CRS grade is determined by the more severe event: hypotension or hypoxia not attributable to any other cause. For example, a patient with temperature of 39.5 °C, hypotension requiring 1 vasopressor, and hypoxia requiring low-flow nasal cannula is classified as grade 3 CRS.

^c Low-flow nasal cannula is defined as oxygen delivered at \leq 6 L/minute. Low flow also includes blow-by oxygen delivery, sometimes used in pediatrics. High-flow nasal cannula is defined as oxygen delivered at \geq 6 L/minute.

- Bronchospasm
- Confusion, mental status changes, and/or delirium
- Dizziness
- Fatigue (asthenia, lethargy, malaise)
- Hallucinations
- Headache
- Hypertension
- Myalgia
- Nausea and/or vomiting
- Rigors/chills
- Diaphoresis
- Tachycardia

Cytokine release syndrome, on the other hand, is more likely to occur after the first dose or first escalated dose of drug than after subsequent doses. It may begin somewhat later and is more likely to be associated with hepatic and neurologic complications, including the following:

- Any of the hypersensitivity signs or symptoms listed above
- Aphasia or word-finding difficulty
- Elevated d-dimer and/or hypofibrinogenemia
- Fatigue (asthenia, lethargy, malaise)
- Gait disturbance/dysmetria
- Hallucinations
- Seizures
- Transaminitis and/or hyperbilirubinemia
- Tremor

The Xencor Medical Monitor should be contacted immediately if questions arise concerning the grade and/or treatment of the infusion reaction.

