7.8. Criteria for Adverse Events of Specific Concern and Dose Adjustment

The National Cancer Institute's (NCI's) Common Terminology Criteria for Adverse Events (CTCAE), Version 5.0, will be used for grading toxicities, except for CRS, which will be graded using the CRS revised grading system (Section 11.2 or Appendix C; Lee, 2014).

An AESC is defined as an AE or clinically significant abnormal laboratory value (unless clearly attributable to underlying malignancy or concurrent disease) occurring after the initiation of dosing and meeting the criteria listed below:

For Parts A, B, and C:

1. Any Grade 5 toxicity

Version 1.0 Page 51 of 145

- 2. Grade \geq 3 thrombocytopenia lasting \geq 7 days or \geq Grade 3 thrombocytopenia of any duration if associated with \geq Grade 3 bleeding
- 3. Grade 4 neutropenia or Grade 3 febrile neutropenia lasting ≥ 7 days, or Grade 4 febrile neutropenia
- 4. Any \geq Grade 3 nonhematological toxicity, **except**:
 - a. Grade 3 fatigue, asthenia, fever, anorexia, or constipation
 - b. Grade 3 nausea, vomiting, diarrhea, or abdominal pain controlled by medical management that decreases to \leq Grade 2 within \leq 7 days
 - c. Grade 3 alanine aminotransferase (ALT) and/or aspartate aminotransferase (AST) that decrease to \leq Grade 2 within \leq 5 days
 - d. Grade ≥ 3 gamma glutamyl transferase (GGT), unless it occurs with AST, ALT, and/or total bilirubin values that meet AESC criteria
 - e. Grade 3 electrolyte abnormalities that are clinically insignificant, or treatable, and that resolve, with or without intervention, to < Grade 2 in < 72 hours
 - f. Grade 3 or 4 lipase values that are not accompanied by ≥ Grade 3 amylase values or clinical symptoms or radiographic evidence of pancreatitis

Additional Criterion for Part B (combination therapy) only:

1. Any immune related adverse event (IRAE) that requires permanent discontinuation of study drug according to the guidelines in Table 18

Subjects who experience any toxicity should be followed until the toxicity stabilizes or has returned to their baseline level, or until the commencement of a new anticancer treatment.

Refer to Section 10.3 for safety criteria for adjustment or stopping XmAb18087 and pembrolizumab.

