14.3. Study Endpoints

14.3.1. Primary Endpoints

The primary endpoints are as follows:

- Safety of (1) XmAb18087 monotherapy in MCC and SCLC, and (2) XmAb18087 and pembrolizumab combination therapy in MCC, as assessed by the following:
 - Incidence of treatment-emergent AEs (TEAEs)
 - Incidence of clinically significant changes in safety laboratory tests, PE findings, vital signs, and ECGs

Version 1.0 Page 99 of 145

- Incidence and severity of CRS
- Efficacy of (1) XmAb18087 monotherapy in MCC and SCLC, and (2) XmAb18087 and pembrolizumab combination therapy in MCC using RECIST 1.1 assessment of CT/MRI imaging, as well as aggregate data, for the following:
 - ORR
 - CR rate
 - PR rate

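### The CRS grading footnote puts nasal-cannula oxygen at exactly 6 L/min in both Grade 2 and Grade 3, with no written tie-break at the grade that makes CRS an AESC

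*Protocol*

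**What the plan says.** Section 11.3.1 and SAP Section 11.1 both grade CRS on the ASTCT consensus scale, which the protocol reproduces as Table 10 and again as Table 15 in Appendix C. In the hypoxia row, Grade 2 is "Requiring low-flow nasal cannula ^c or blow-by" and Grade 3 is "Requiring high-flow nasal cannula c, facemask, nonrebreather mask, or Venturi mask". Footnote c turns the two cannula terms into flow rates: "Low-flow nasal cannula is defined as oxygen delivered at \leq 6 L/minute", and "High-flow nasal cannula is defined as oxygen delivered at \geq 6 L/minute". Footnote c of Table 15 reads the same way. Footnote b adds that "CRS grade is determined by the more severe event: hypotension or hypoxia not attributable to any other cause".

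The grade is used in two places that matter for the analysis. Protocol Section 14.3.1 lists "Incidence and severity of CRS" among the primary safety endpoints, and SAP Section 3.3 lists it as a safety endpoint. Section 7.8 lists as an AESC any event at or above "Grade 3 nonhematological toxicity, except" for items a to f, and CRS is not one of those items. For toxicity grading, Section 7.8 uses CTCAE "except for CRS, which will be graded using the CRS revised grading system" and points the reader to Section 11.2 or Appendix C.

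**The concern.** Two definitions that should divide the cannula flow rates share an endpoint, and that endpoint is the boundary between Grade 2 and Grade 3. A reader who applies the low-flow sentence has a Grade 2 event. A reader who applies the high-flow sentence to the same event has a Grade 3 event.

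This boundary also decides whether CRS is an AESC. AESC counts determine whether a run-in cohort goes to the Safety Review Committee (SRC) after 3 subjects or first enrolls 3 more (Section 7.7), and whether expansion enrollment is suspended (Section 7.8.2). For the individual subject, an AESC triggers the dosing provisions of Section 10.3.1, and Section 11.3.3.3 gives different instructions for Grade 2 and Grade 3 reactions. CRS is not a remote event: Section 5.1.7 expects it as a toxicity of the drug, and up to 25 sites were planned.

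**Working it through.** The plan states no figure to reproduce, so the check sets the definitions side by side and follows the result through the rules that use it.

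**1. The two ranges.** Let x be the nasal-cannula flow in L/min. From footnote c of Tables 10 and 15:

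- low flow: x ≤ 6
- high flow: x ≥ 6
- both at once: x = 6 only

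| Cannula flow | Hypoxia criterion met |
|---|---|
| x < 6 | Grade 2 |
| x = 6 | Grade 2 and Grade 3 |
| x > 6 | Grade 3 |

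There is no gap, and the overlap is a single value.

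**2. How far the overlap reaches.** Footnote c counts blow-by oxygen as low flow. The listed masks are Grade 3 whatever the flow, and positive pressure is Grade 4. By Table 10, hypotension requiring a vasopressor already gives Grade 3 or higher. The ambiguous case is therefore CRS treated by nasal cannula at exactly 6 L/min, without one of the listed masks, positive pressure or vasopressor-requiring hypotension.

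**3. Possible tie-breaks.**

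- Footnote b takes the worse of hypotension and hypoxia. It does not choose between two hypoxia grades.
- Section 11.1.2.1 records the maximum intensity when intensity changes within a day. Here nothing changes: one fixed state meets two definitions.
- SAP Section 11.1 names the scale and adds no rule.
- Section 11.3.2 and Appendix C send questions about the grade to the Medical Monitor. That is a route for resolving doubt, not a rule that assigns the value.

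**4. Link to the AESC definition.** Section 7.8 excludes events clearly attributable to underlying malignancy or concurrent disease. Otherwise Grade 3 CRS is an AESC, and Grade 2 CRS meets no AESC criterion. Of the two pointers in Section 7.8, Section 11.2 concerns IND safety reports and holds no grading table. Appendix C holds Table 15 with the same footnote. The link therefore runs through Appendix C.

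**5. Effect of one such event on the run-in (Section 7.7).**

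| Other AESCs in the first 3 subjects | Read as Grade 2 | Read as Grade 3 |
|---|---|---|
| 0 | 0 AESCs: SRC meets after 3 subjects | 0 + 1 = 1: enroll 3 more, 3 + 3 = 6, then SRC |
| 1 | 1 AESC: enroll 3 more, then SRC | 1 + 1 = 2: no further enrollment until SRC meets |

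**6. Effect of one such event in expansion (Tables 5 and 6).** The boundary is 3 at n = 3, 4 and 5. With two other AESCs the count is 2 + 0 = 2, below the boundary, or 2 + 1 = 3, which meets it and suspends enrollment until the SRC has met.

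**7. What remains live.** SAP Section 5.1 reports 2 + 2 = 4 subjects, in Parts A and C. Neither Part reached the 3 subjects at which a run-in cohort's initial enrollment is complete and at which the expansion boundaries begin. SAP Sections 5.1 and 10 plan listings only.

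**8. After correction.** If either bound is made strict in both footnotes, no flow meets both definitions and every cannula flow maps to one hypoxia grade.

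**The case against.** The strongest objection is provenance. The point turns on one inequality sign, and the text was read from PDF by a program. That the two copies agree is limited reassurance, because the same program read the same sentence twice. Other signs in the text are doubtful: the lymph-node size in the RECIST appendix has lost one (P10 to < 15 mm), and the AST limit with liver metastases is ≥ 7 × ULN in the synopsis but > 7 × ULN in Section 8.6. This objection stands to the extent that the source page must be checked first.

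The second objection is that grading doubts go to one central role, the Medical Monitor. That stands in part. A reader might infer that sites are free to grade the same event differently, but the documents do provide a route to a single answer. The route works only if someone notices the conflict; a site that applies one of the two sentences already has a grade and no evident reason to ask.

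The third is consequence. The SRC reviews all available safety data, not the AESC count alone, and crossing an expansion boundary suspends enrollment rather than ending the cohort. A reader might infer that the AESC monitoring as a whole is unreliable. The documents do not support that: the overlap is one flow value on one device, and no frequency of its use is given. Nor is the AESC link unconditional. The text of Section 7.8 cites an older CRS grading reference than the one in Section 11.3.1, and only its Appendix C pointer leads to this footnote.

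**Conclusion.** As transcribed, the grading rule contradicts itself at 6 L/min, and nothing written assigns that value to Grade 2 or Grade 3. One affected event would change its recorded severity by one grade and add 0 or 1 to an AESC count. That is enough to move a run-in cohort from one path to the next, or to reach a boundary of 3 when two other AESCs have occurred.

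The practical effect is now small. The case is narrow, its frequency is unknown, and with 4 subjects and listings only the most that can change in the report is the grade, and any AESC flag, of an individual event. A reader might infer that a listed grade or an enrollment decision was in fact affected; the documents do not say that any event was treated at this flow.

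The conclusion assumes that the transcribed signs match the source PDF and that CRS is graded for AESC purposes on the table in Appendix C.

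**What to change.** 1. Check both signs in footnote c of Tables 10 and 15 against the source PDF. If they do not overlap there, the point falls.
2. If they do, reconcile the two definitions so that the flow ranges are mutually exclusive, with the same wording in both footnotes. Which grade 6 L/min belongs to is for the sponsor's clinicians to decide.
3. For the 4 enrolled subjects, identify any CRS event treated by nasal cannula at 6 L/min, and check that its listed grade and AESC status follow the reconciled rule.

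The cost is one symbol in each of two footnotes and a short look at the CRS records of 4 subjects. The correction should also carry into any later document that reuses the table. The eCRF was not available for this review, so whether flow rate is already recorded is unknown; if it is not, step 3 needs source records.
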